## 7.5. Study Documentation and Archival

The investigator should maintain a list of appropriately qualified persons to whom he/she has delegated study duties. All persons authorized to make entries and/or corrections on case report forms will be included on the Delegation of Authority Form.

Source documents are original documents, data, and records from which the subject's case report form data are obtained. These include but are not limited to hospital records, clinical and office charts, laboratory and pharmacy records, diaries, microfiches, radiographs, and correspondence. Case report form entries may be considered source data if the CRF is the site of the original recording (ie, there is no other written or electronic record of data). In this study, case report forms calculating IPSS may be used as source documents for IPSS risk category assignment.

The investigator and study staff are responsible for maintaining a comprehensive and centralized filing system of all study-related (essential) documentation, suitable for inspection at any time by representatives from Calithera and/or applicable regulatory authorities. Elements should include:

- Subject files containing completed case report forms, informed consent forms, and subject identification list
- Study files containing the protocol with all amendments, investigator's brochure, copies of prestudy documentation and all correspondence to and from the IEC/IRB and Calithera
- Proof of receipt, Investigational Product Accountability Record, Return of Investigational Product for Destruction, Final Investigational Product Reconciliation Statement, and all drug-related correspondence

In addition, all original source documents supporting entries in the case report forms must be maintained and be readily available. No study document should be destroyed without prior written agreement between Calithera and the investigator. Should the investigator wish to assign the study records to another party or move them to another

NCT ID: NCT03047993

Protocol 2016-0636 ate: 06/03/2019 Version 1

Page **32** of **39** 

location, he/she must notify Calithera in writing of the new responsible person and/or the new location.

## 7.6. Serious Adverse Event Reporting (SAE):

See Section 6.2.4 for detailed information regarding SAE definitions.

It is the responsibility of the PI and the research teams to ensure serious adverse events are reported according to the Code of Federal Regulations, Good Clinical Practices, the protocol guidelines, the sponsor's guidelines, and Institutional Review Board policy.

All events occurring during the conduct of a protocol and meeting the definition of a SAE must be reported to the IRB in accordance with the timeframes and procedures outlined in "The University of Texas M. D. Anderson Cancer Center Institutional Review Board Policy for Investigators on Reporting Unanticipated Adverse Events for Drugs and Devices". Unless stated otherwise in the protocol, all SAEs, expected or unexpected, must be reported to Calithera, regardless of attribution (see Section 6.2.2.3). SAE reporting will be done according to 21 CFR 312.32(c)(1)(iv) ("Sponsor must report any clinically important increase in the rate of a serious adverse reaction over that listed in the protocol or investigator brochure.").

The descriptions and grading scales found in the revised NCI Common Terminology Criteria for Adverse Events (CTCAE) version 4.03 will be utilized for adverse event reporting. (http://ctep.cancer.gov/reporting/ctc.html).

#### 7.7 IND Summaries:

A Toxicity Summary will be submitted to the IND Office Medical Monitor after the first six evaluable patients complete cycle one of study treatment, prior to the Dose modification or Phase II.

A Toxicity Summary will be submitted to the IND Office Medical Monitor after the first 7 evaluable patients and every 7 evaluable patients thereafter.

A Response Summary will be submitted to the IND Office Medical Monitor after 16 evaluable patients complete 6 cycles of study treatment.

#### 8. STATISTICAL CONSIDERATIONS:

Protocol 2016-0636 ate: 06/03/2019 Version 1

Page 33 of 39

### 8.1. Statistical Design

This is a single institution phase Ib/II study to determine the safety, tolerability and clinical activity of telaglenastat in combination with azacitidine (AZA) for patients with advanced MDS. Up to 40 patients will be enrolled from MDACC, allowing 6 patients treated in the Phase 1b portion that are removed from study before day 28 for any reason other than toxicity and have not experienced DLT, or considered non-evaluable for DLT or response.

#### 8.1.1 Phase lb:

The Phase Ib part of the study is performed to assess the safety of telaglenastat in combination with AZA. We will first enroll 6 patients at dose level 0. If only 0 or 1 of 6 patients experiences a DLT, the dose level will be identified as the RP2D. If at least 2 of 6 patients experience DLTs, then the MTD has been exceeded and 6 patients will be treated at the lower dose level (i.e. dose level -1). If at least 2 of 6 patients experience DLTs in dose level -1, the combination may be considered too toxic in this indication and the study may be discontinued. The 6 patients treated at the RP2D level will be evaluated in the Phase II portion. A maximum of 12 patients will be enrolled in the Phase 1b part of the study.

A Toxicity Summary will be submitted to the IND Office Medical Monitor after the first six evaluable patients complete cycle one of study treatment, prior to the Dose modification or Phase II.

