Table 1: CX-839-003 Treatment-Related Adverse Events in ≥ 2 patients - BID fed

BID Monotherapy (N=11)			
MedDRA Preferred Term		Number (%) of patients	
Medbix Freiened Teini	All Grades	≥Grade 3	
Patients with Any CB-839-Related AE	9 (81.8)	5 (45.5)	
THROMBOCYTOPENIA	4 (36.4)	4 (36.4)	
ASPARTATE AMINOTRANSFERASE INCREASED	2 (18.2)	0	
BLOOD CREATININE INCREASED	2 (18.2)	0	
CONSTIPATION	2 (18.2)	0	
DYSPNOEA	2 (18.2)	0	
NEUTROPENIA	2 (18.2)	2 (18.2)	

Reductions in blast counts were achieved in 2 patients with AML receiving monotherapy telaglenastat including one with CRi.

NCT ID: NCT03047993 Protocol 2016-0636 ate: 06/03/2019

Version 1

Page **11** of **39** 

On the CX-839-003 study telaglenastat also is being evaluated at escalating doses (400 mg BID – 800 mg BID) in combination with standard dose azacitidine (75 mg/m^2 dosed IV or SC for 7 days of every 28-day cycle). As of the data cutoff for this document 4 patients have received telaglenastat in the 400 mg BID dose cohort in combination with azacitidine One of 4 patients has experienced a treatment-related AE considered at least possibly related to telaglenastat. To date, no DLTs have occurred. Efficacy data are not yet available for patients receiving telaglenastat in combination with azacitadine.

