#### 4.1.1. Phase 1b:

In the Phase 1b portion, telaglenastat will be administered at the goal starting dose level 0 of 600mg BID continuously. The MTD is defined as the highest dose level with </= 1 out of 6 patients experiencing a DLT during the first cycle.

The first 6 patients will be treated at dose level 0. If </= 1 out of the 6 patients experience a DLT during the first cycle, this level will be identified as the RP2D and the study will progress to the Phase II portion. If > 2 out of the 6 patients experience a DLT during the first cycle, this dose level would exceed the MTD, and an additional 6 patients will be treated at the next lower dose level. Reduced dose level -1 is defined in Table 1 below. Patients treated in the Phase 1b portion that are removed from study before day 28 for any reason other than toxicity, and have not experienced DLT, will be replaced.

AZA will be administered subcutaneously (SQ) or intravenously (IV) for 7 days of every cycle (days 1-7) as determined by the treating physician. Both SQ and IV forms of administration are FDA-approved and are considered interchangeable, based on patient and physician preference.

Table 1: Dose de-escalation for telaglenastat and AZA

Dose Level	CB-839 (oral)	AZA (IV or SQ)
0	600 mg BID days 1-28	75 mg/m2 days 1-7
-1	400 mg BID days 1-28	75 mg/m2 days 1-7

Dose reductions beyond those mentioned in this table or different to the doses specified should be discussed with the PI and documentation of the justification recorded in the medical record.

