#### 4.1.1.2. Dose De-escalation Procedures:

A dose-limiting toxicity (DLT) is defined as any Grade 3 or higher non-hematologic adverse event or abnormal laboratory value occurring during the first cycle (i.e. the first 28 days) on study except those that are clearly and incontrovertibly due to disease progression or extraneous causes, with the following exceptions:

Protocol 2016-0636 ate: 06/03/2019

Page **14** of **39** 

 CTCAE v4.03 Grade 3 AST or ALT that resolves to < Grade 2 within 14 days
 without an associated rise in bilirubin

- Grade 3 nausea, vomiting or diarrhea that can be managed to < Grade 2 with
 standard antiemetic or antidiarrheal medications
- Grade > 3 electrolyte abnormality that lasts < 24 to 72 hours, is not clinically complicated, and resolves spontaneously or responds to conventional medical interventions
- Grade 3 biochemical abnormalities of amylase or lipase without clinical evidence of pancreatitis

Hematologic DLT is defined as Grade > 3 neutropenia and/or thrombocytopenia with a hypocellular bone marrow lasting for 6 weeks or more after the start of a course in the absence of underlying MDS. Anemia will not be considered for the definition of DLT.

**4.1.1.3**. The first 6 patients will be treated at dose level 0. If DLT occurs in > 2/6 evaluable patients, this dose level would exceed the MTD, and an additional 6 patients will be treated at the lower dose level. The highest dose level at which 0-1/6 patients experience DLT will be used as the RP2D. Should >2/6 DLTs occur in dose level -1, the combination may be considered too toxic in this indication and the study may be discontinued.

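### Phase 1b has no rule that closes a dose level to new patients once its own condition of 0-1 DLTs in 6 can no longer be met

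*Combined protocol and SAP*

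**What the plan says.** Section 4.1.1 opens the dose-finding part with "The first 6 patients will be treated at dose level 0", and Section 8.1.1 repeats the block of six: "We will first enroll 6 patients at dose level 0". The passing condition is the same wherever it appears:

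- Section 4.1.1: "The MTD is defined as the highest dose level with </= 1 out of 6 patients experiencing a DLT during the first cycle".
- Section 4.1.1.3: "The highest dose level at which 0-1/6 patients experience DLT will be used as the RP2D".
- Section 8.1.1: "If only 0 or 1 of 6 patients experiences a DLT, the dose level will be identified as the RP2D".

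Section 4.1.2 adds that the RP2D may not exceed the MTD. The failing condition is printed in two ways. Section 8.1.1 has "If at least 2 of 6 patients experience DLTs, then the MTD has been exceeded", while Sections 4.1.1 and 4.1.1.3 print a trigger of more than 2 of 6. The same structure applies at level -1.

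On review, Section 7.7 says "A Toxicity Summary will be submitted to the IND Office Medical Monitor after the first six evaluable patients complete cycle one", and Section 8.1.1 repeats it. No other cohort-level toxicity review is named for Phase 1b. The Bayesian rule in Section 8.1.3 is for Phase II and is first applied at the 7th patient.

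**The concern.** After two DLTs at a level, no result from the remaining patients can bring the count back to 0 or 1 of 6, so the dose decision is already made. The plan does not say what then happens to enrolment at that level, and its one formal review point waits for six evaluable patients. A team following the text literally could start up to four more patients at that level, before any replacements for non-evaluable patients. Their outcomes could not change whether the level passes. What is at stake is avoidable exposure of a small number of patients. No error rate, efficacy analysis or dose decision is affected.

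**Working it through.** **The plan's own toxicity figures.** The documents give no operating characteristics for the Phase 1b rule. The nearest figures are Tables 1 and 2 of Section 8.1.3. With a beta(0.6, 1.4) prior and x toxicities in n patients, the posterior is beta(0.6 + x, 1.4 + n - x). The posterior probability of a rate above 0.30 is 0.901 at 4/7, 0.9245 at 7/14 and 0.944 at 10/21; it is 0.818 at 6/14 and 0.876 at 9/21. The printed boundaries 4, 7 and 10 follow. Exact binomial recursion over looks at 7, 14 and 21 with a maximum of 28 returns the printed stopping probabilities 0.0028, 0.0398, 0.1817, 0.4639 and 0.7697. These figures are right, but they describe Phase II only.

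**Inputs.**
- Cohort of 6, passing with 0-1 DLTs (Sections 4.1.1, 4.1.1.3, 8.1.1).
- True DLT rate p: not given, so assumed at 10% to 40%, within the 0.10 to 0.50 range of Table 2 in Section 8.1.3.
- Accrual speed: not given. First taken as strictly sequential, with each outcome known before the next patient starts; then relaxed.

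**Formulas.**
- P(level fails) = 1 - (1-p)^6 - 6p(1-p)^5.
- P(second DLT falls on patient k) = (k-1)p²(1-p)^(k-2), for k = 2 to 6.
- Expected patients treated after the second DLT = sum over k of (6-k)(k-1)p²(1-p)^(k-2).
- Given that the level fails: the previous line divided by P(level fails).
- If m further patients have already started when the second DLT is known, 6-k becomes 6-k-m, with a floor of 0.

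**Worked case, p = 0.3.**
- P(level fails) = 1 - 0.1176 - 0.3025 = 0.580.
- Expected after the second DLT = 4(0.09) + 6(0.09)(0.7) + 6(0.09)(0.49) + 4(0.09)(0.343) = 0.360 + 0.378 + 0.265 + 0.123 = 1.13.
- Given failure: 1.126 / 0.580 = 1.94.
- With m = 1: 3(0.09) + 4(0.09)(0.7) + 3(0.09)(0.49) = 0.270 + 0.252 + 0.132 = 0.65.
- With m = 2: 2(0.09) + 2(0.09)(0.7) = 0.180 + 0.126 = 0.31.

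**Results per level.**

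| True DLT rate | P(level fails) | Expected treated after second DLT | Same, given the level fails | Expected spared, m = 1 | Expected spared, m = 2 |
|---|---|---|---|---|---|
| 10% | 0.114 | 0.17 | 1.50 | 0.09 | 0.04 |
| 20% | 0.345 | 0.59 | 1.70 | 0.32 | 0.14 |
| 30% | 0.580 | 1.13 | 1.94 | 0.65 | 0.31 |
| 40% | 0.767 | 1.70 | 2.22 | 1.04 | 0.51 |

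With m = 4, that is, all six started before the second DLT is known, nobody is spared.

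**Effect of early closure on the decision.** A level fails the 0-1 of 6 condition exactly when a second DLT occurs among the six. Closing at that moment leaves P(level fails) as shown, for every possible sequence of outcomes.

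**Could another rule fill the gap?** The Bayesian rule does not look before the 7th patient. Section 7.7 also has a summary after every 7 evaluable patients. Even if Phase 1b patients counted towards it, the 7th would be the first at level -1, before a second DLT there is possible.

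**The case against.** The strongest reply is that silence is not an instruction. Nothing obliges the team to go on enrolling after a second DLT, and the trigger in Section 8.1.1 is in substance met at that point. Toxicity is also watched well before the sixth patient finishes. There are AE checks and laboratory tests on days 8, 15 and 22 of cycle 1 (Section 5.2.3). SAEs go to the IND Office within 5 working days, and within 24 hours if unexpected, related and life-threatening or fatal (Section 6.2.4). They also go to the company (Section 6.2.6), and either the company or the investigator may terminate the study (Section 7.4). All of this stands. A reader might infer that the plan ignores toxicity until the sixth patient completes cycle 1, or that it orders continued exposure. The documents support neither reading. They support only that no rule governs enrolment to the level in the meantime.

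The objection on size also stands in part. Strictly sequential entry would take 6 × 28 = 168 days for one cohort, and some DLTs are called late. Section 4.1.1.2 excuses Grade 3 AST or ALT that resolves within 14 days, and its hematologic criterion needs cytopenia lasting at least 6 weeks from the start of a course, which is beyond day 28. Both reduce what early closure can save.

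Two further inferences are tempting and fail:

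- That the extra patients use up places under the cap of 40. The cap already covers a full failed cohort: 12 in Phase 1b (Section 8.1.1) + 22 in Phase II (Section 4.1.2) + 6 allowed for (Section 8.1) = 40.
- That the gap is worse because level 0 is above the 400 mg BID combination cohort in Section 2.7. That section also reports monotherapy experience at higher doses and a combination study running up to 800 mg BID, and none of it bears on when a cohort should close.

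**Conclusion.** The gap is real but small. The plan permits, without requiring, new patients to start at a level that can no longer be the RP2D. The expected numbers treated after the second DLT (0.17 to 1.70 per level at assumed DLT rates of 10% to 40%) are upper bounds on what early closure could spare. They assume independent patients with a common DLT rate, strictly sequential entry, immediate ascertainment and no replacements. The larger figures of 1.50 to 2.22 apply only when the level fails and should not be quoted alone. With one or two patients already started, the saving at a 30% rate falls from 1.13 to 0.65 or 0.31.

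The conclusion does not depend on whether the failing trigger is at least 2 or more than 2 of 6, because every section requires 0-1 of 6 for the RP2D. Read literally, however, the Section 4 wording leaves a result of exactly 2 of 6 neither passing nor triggering de-escalation. The sign may have been lost when the PDF was read. Minor severity: a cheap improvement.

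**What to change.** In Sections 4.1.1, 4.1.1.3 and 8.1.1, state that new enrolment to a dose level closes once confirmed DLTs mean that the plan's own 0-1 of 6 condition can no longer be met, without waiting for six evaluable patients. In Sections 7.7 and 8.1.1, state that the Toxicity Summary is submitted at that time or after six evaluable patients complete cycle 1, whichever comes first. In the same edit, reconcile the failing trigger in Sections 4.1.1 and 4.1.1.3 with that in Section 8.1.1.

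The dose levels, the DLT definition and the 0-1 of 6 decision stay as they are. The cost is a few sentences, prompt notification of each DLT within the study team and to the medical monitor, and a less precise DLT estimate at a level already rejected.

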#### 8.1.2. Phase II:

The Simon minimax two-stage design will be employed for the Phase II portion.(15) We assume a target response rate of 60% and a response rate of 40% or lower will be considered not desirable. Response is defined as complete remission (CR), partial remission (PR), marrow CR (mCR), or Hematologic Improvement (HI) by modified IWG criteria for MDS patients. For example a 29% CR/PR rate was reported in the azacitidine arm in the randomized AZA-001 trial, and a 23% CR/PR rate and 60% ORR (including 37% HI) was seen in the azacitidine arm of the CALGB 9221 trial. To implement the Simon's two-stage design, the assessment window for response (CR+PR+mCR+HI) is defined as response occurring within the first 6 cycles of treatment. With a type I error rate of 10% and 80% power, we will enroll 16 patients in the first stage. If 6 or fewer patients achieve response, enrollment will be halted. If 7 or more out of the first 16 patients achieve response, accrual will continue until a total of 28 patients have been enrolled. If 15 or more out of these 28 patients achieve response, the treatment will be considered efficacious and worthy of further investigation. Under this Simon's minimax two-stage design, the probability of early termination is 53% and the expected sample size is 22 if the true response rate is 40%.

Protocol 2016-0636 Date: 06/03/2019

Page **34** of **39** 

A Toxicity Summary will be submitted to the IND Office Medical Monitor after the first 7 evaluable patients and every 7 evaluable patients thereafter.

A Response Summary will be submitted to the IND Office Medical Monitor after 15 evaluable patients complete 6 cycles of study treatment.

### **8.1.3. Toxicity:**

The method of Thall, Simon and Estey will be used for toxicity monitoring for the Phase II part of this study.(16) For monitoring purposes, toxicity is defined as DLT which occurs during the first cycle. Denote the probability of toxicity by  $P_T$ . We assume as a priori,  $P_T \sim$  beta (0.6, 1.4). Our stopping rule is to stop the trial if  $Pr(P_T > 0.30 \mid data) > 0.90$ . That is, we will stop the trial for new patient enrollment if at any time during the study; we determine that there is more than 90% chance that the toxicity rate is more than 30%. This toxicity stopping rule will be applied in cohort size of 7, starting from the 7th patient. Stopping boundaries corresponding to this stopping rule are listed in Table 1. The operating characteristics are summarized in Table 2. The design software Multc Lean Desktop (version 2.1) developed by the Department of Biostatistics at M. D. Anderson Cancer Center (MDACC) was used to generate the toxicity stopping boundaries and the operating characteristics table.

Table 1. Early stopping boundaries for toxicity monitoring

# of patients ( in cohort size of 7, starting from the 7 th patient)	Stop the trial if there are this many patients with toxicities:
7	4-7
14	7-14
21	10-21

Table 2. Operating characteristics for toxicity monitoring

True toxicity rate	Prob(stop the trial early)	Average sample size
0.10	0.0028	27.94
0.20	0.0398	27.22
0.30	0.1817	24.69
0.40	0.4639	19.91
0.50	0.7697	14.37

NCT ID: NCT03047993

Protocol 2016-0636 ate: 06/03/2019

Page **35** of **39** 

### 8.2 Analysis Populations:

## 8.2.1. Safety Population

All patients who receive at least 1 dose of telaglenastat will be included in the analysis of safety regardless of the duration of treatment. Patients who experience adverse events during the Screening period but who do not start on study treatment due to reasons that include, but are not limited to ineligibility/screen failure, death or withdrawal of consent, will not be included in the safety population.

#### 8.2.2. DLT-evaluable:

Unless doses are missed in Cycle 1 due to DLT(s), a patient must receive at least 85% of the planned doses of telaglenastat and at least  $\geq$  5 doses of azacitidine to be considered evaluable for DLTs. If a patient received fewer doses of telaglenastat or AZA in the first 28 days of treatment for reasons other than a DLT, the patient will be considered non-evaluable for DLT and replaced.

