# 4.5 Dosing Delays and Dose Modifications:

## 4.5.1. Dose Adjustments:

The doses of telaglenastat and AZA will be adjusted according to the guidelines shown in the following tables for study drug-related clinically significant toxicity. If toxicity is not covered in the table, doses may be reduced or held at the discretion of the investigator for the patient's safety.

Patients will be withdrawn from the study if they fail to recover to CTCAE v4.03 grade 0 to 1 (or within 1 grade of starting values for pre-existing laboratory abnormalities) from a clinically significant non-hematologic treatment-related toxicity within 6 weeks (leading to treatment delay of > 4 weeks) unless the investigator feels that the patient should remain in the study because of evidence that the patient is/may continue deriving benefit from continuing study treatment. Such instances will be discussed with the principal investigator on a case by case basis and the discussion documented in the medical record.

Protocol 2016-0636 Date: 06/03/2019

Page **18** of **39** 

Patients with study-drug related toxicities that are manageable with supportive therapy may not require dose reductions. For patients with other drug-related toxicities, the following dose adjustment rules apply:

	NCI CTCAE v4.03 Grade	Action
	Grade 0-2 non-hematological toxicity	No dose reduction.  For grade 2 toxicities that are persistent and/or intolerable (e.g. stomatitis) patients may
		have a treatment interruption or dose reductions to the next lower dose level.
4.5.2.	Grade 3-4 clinically significant non-hematological toxicity†	Hold until recover to NCI CTC AE grade 0-1
		If recovery occurs within 4 weeks after treatment has been held, dose should be reduced to -1 dose level, if applicable.

Administration of subsequent cycles should be administered when neutrophils recover to  $\geq 1 \times 10^{9}$ /L and platelets to  $\geq 30 \times 10^{9}$ /L, or to baseline levels prior to the start of the last cycle of therapy. Patients with residual disease may start the next cycle with neutrophil and/or platelet counts lower than these if judged to be in the best interest of the patient. The decision to treat should be documented in the patient's medical record.

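### Read literally, Section 8.2.2 drops a cycle 1 DLT from the Phase Ib count when a patient who stays on study fell below the dosing minimum for another reason

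*Combined protocol and SAP*

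**What the plan says.** Section 8.2.2 sets the minimum and its only waiver: "Unless doses are missed in Cycle 1 due to DLT(s), a patient must receive at least 85% of the planned doses of telaglenastat", together with at least 5 azacitidine doses. The next sentence deals with a shortfall. Its condition is "If a patient received fewer doses of telaglenastat or AZA in the first 28 days of treatment for reasons other than a DLT"; the stated consequence is that "the patient will be considered non-evaluable for DLT and replaced".

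Two other places deal with replacement, and both make the absence of a DLT a condition:

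- Section 4.1.1 covers Phase 1b patients "removed from study before day 28 for any reason other than toxicity, and have not experienced DLT, will be replaced".
- Section 8.1 sets aside places for patients "removed from study before day 28 for any reason other than toxicity and have not experienced DLT, or considered non-evaluable for DLT or response". Non-evaluable patients appear here as a separate category, which leads back to 8.2.2.

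Section 4.1.1.3 applies the Phase Ib rule to evaluable patients. Section 8.1.1 states the rule: 0 or 1 DLT in 6 makes the level the RP2D, and 2 or more means that the MTD has been exceeded. For Phase II monitoring, Section 8.1.3 says that "toxicity is defined as DLT which occurs during the first cycle" and attaches no dosing condition.

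**The concern.** A dosing minimum guards against reading too little exposure as tolerance, so it is needed for patients without a DLT. A patient who had a DLT on reduced exposure has already given the information that the cohort is meant to collect. Section 8.2.2 does not make that distinction.

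The situation can arise under the plan's own rules. The dose adjustment table in Section 4.5 permits an interruption "For grade 2 toxicities that are persistent and/or intolerable", and a non-hematologic Grade 2 event is below the DLT threshold in 4.1.1.2. Suppose such a patient is interrupted, resumes, and later in cycle 1 has an event that meets the DLT definition. The earlier shortfall was not caused by that DLT. At stake is a decision on six patients that a single event can reverse, and the six patients at the RP2D are carried into the Phase II evaluation.

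**Working it through.** **Plan's own figures first.** Section 8.2.2 states no computed figure. The stated figures that rest on a DLT count are those in 8.1.3. With a Beta(0.6, 1.4) prior, the posterior is Beta(0.6 + x, 1.4 + n − x). Pr(P_T > 0.30) is 0.901 at 4/7, 0.925 at 7/14 and 0.944 at 10/21. One toxicity fewer gives 0.717, 0.818 and 0.876. The boundaries 4, 7 and 10 reproduce, as do all five early-stopping probabilities and average sample sizes. Nothing there needs correction.

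**Dosing threshold.** Section 4.1.1 plans two telaglenastat doses a day for 28 days: 2 × 28 = 56. Then 0.85 × 56 = 47.6, so 48 doses are needed (48/56 = 85.7%; 47/56 = 83.9%). Nine missed doses, or 4.5 days, fall short; a five-day interruption misses 10. For azacitidine 7 doses are planned and 5 required, so 3 missed doses fall short.

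**Who is caught, reading the sections together.**

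| Patient with a cycle 1 DLT | Governing text | Result |
|---|---|---|
| Removed before day 28 for a reason other than toxicity | 4.1.1, 8.1 | Not replaced under these sections |
| Stays on study; shortfall due to the DLT | 8.2.2 waiver | Counted |
| Stays on study; shortfall wholly for another reason | 8.2.2, second sentence | Non-evaluable, replaced |
| Stays on study; doses missed for both reasons | 8.2.2, both sentences | Ambiguous |

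**Effect on one cohort.** Two DLTs in 6 exceed the MTD. If one is discarded and the replacement has no DLT, the count reads 1/6 and the level becomes the RP2D.

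**Effect on the pass probability.** Let p be the true DLT rate and q the share of DLT patients discarded. The documents give no q, so the values below are assumptions. If no patients without a DLT are replaced, the rate among counted patients is

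p′ = p(1 − q) / [p(1 − q) + (1 − p)] = p(1 − q)/(1 − pq),

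and P(0-1 of 6) = (1 − p′)^6 + 6p′(1 − p′)^5.

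At p = 0.30 and q = 0: 0.7^6 + 6 × 0.3 × 0.7^5 = 0.1176 + 0.3025 = 0.420. At q = 0.10: p′ = 0.27/0.97 = 0.278.

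| q | p′ | P(0-1 of 6) |
|---|---|---|
| 0 | 0.300 | 0.420 |
| 5% | 0.289 | 0.443 |
| 10% | 0.278 | 0.468 |
| 20% | 0.255 | 0.521 |

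At q = 10%, the same step takes P(0-1 of 6) from 0.655 to 0.695 at p = 0.20 and from 0.233 to 0.274 at p = 0.40.

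**Allowing for replaced patients without a DLT.** If a share u of them is also replaced, the counted rate is p(1 − q)/[p(1 − q) + (1 − p)(1 − u)]. With q = u this equals p. The downward bias therefore requires DLT patients to be lost in a larger proportion than the others.

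**Phase II, only if 8.2.2 governs it.** At p = 0.30 the early-stopping probability would fall from 0.1817 to 0.1595, 0.1384 or 0.1004 for q of 5, 10 or 20%.

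**The case against.** The strongest reply is that the text need not lose the patient. The opening waiver does not require all, or even most, of the missed doses to be due to the DLT. The table in Section 4.5 holds treatment after clinically significant Grade 3-4 non-hematologic toxicity. A patient with an earlier shortfall who then has such a DLT would normally miss further doses because of it, which may trigger the waiver. This stands: mixed reasons are ambiguous, not a settled discard. The clear residue is a DLT that causes no further missed dose, for example late in the cycle or a laboratory value that does not lead to a hold. That group is small.

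Second, Sections 4.1.1 and 8.1 show an intent to keep DLT patients. That also stands, but both tie the condition to removal before day 28, so they do not reach a patient who remains on study.

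Third, there are safeguards. The event stays in the safety population (8.2.1), RP2D selection draws on the totality of the data (4.1.2), and a toxicity summary precedes Phase II (7.7). These soften the consequence, but the 0-1 of 6 count is still made on evaluable patients.

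A reader might go further and infer a large bias by supposing that DLT patients are under-dosed for other reasons far more often than the rest. Nothing in the documents supports such a ratio. A reader might also infer that the Phase II stopping rule is biased. Section 8.1.3 carries no dosing condition; the toxicity summaries in 7.7 and 8.1.2 refer to evaluable patients, but no section says that 8.2.2 governs the monitoring.

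**Conclusion.** The point holds as a gap in 8.2.2 and a conflict with the evident intent of 4.1.1 and 8.1. As written, a patient who stays on study, falls below the minimum wholly for a reason other than a DLT, and has a cycle 1 DLT drops out of the Phase Ib count. It would be wrong to conclude that every under-dosed DLT patient is discarded, or that the 15% margin applies to both drugs; it is a telaglenastat criterion, and azacitidine has its own 5-dose minimum.

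The affected group is narrow. The size is a scenario, not an estimate: at a true DLT rate of 30%, discarding 5 to 20% of DLT patients raises the chance of 0-1 in 6 from 0.42 to between 0.44 and 0.52, taking no replacement of patients without a DLT. It is worth correcting because one event can reverse the dose-level decision and the correction is short. Any effect on Phase II monitoring remains open until the plan says which definition applies.

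**What to change.** Add to 8.2.2 a sentence to this effect: *any patient who has received study treatment and has a DLT in cycle 1 is DLT-evaluable and is not replaced, whatever the doses received; the 85% telaglenastat and 5-dose azacitidine minimum applies only to patients without a DLT.* This also settles the mixed-reason case. Align the replacement wording in 4.1.1 and 8.1 with it, and state whether the same definition applies to the toxicity monitoring in 8.1.3.

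The decision rule, sample size and stopping boundaries stay as they are. The cost is a somewhat conservative count, because under-dosed patients without a DLT are still replaced. If 10, 20 or 30% of them were (assumption), the counted rate at a true 30% would be 0.30/0.93 = 32.3%, 0.30/0.86 = 34.9% or 0.30/0.79 = 38.0%, and P(0-1 of 6) would be 0.37, 0.32 or 0.27 against 0.42. The plan should accept that openly.
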